#### **5.1.4. Microbiologic Outcome**

##### **5.1.4.1. Per-Pathogen Microbiologic Outcome**

Microbiologic outcome at Day 5, EOT, and TOC will be programmatically determined for each pathogen isolated at baseline. Per-pathogen microbiological response categories are eradication, persistence, and indeterminate defined as following:

Microbiologic eradication: the demonstration that the baseline bacterial pathogen(s) is reduced to  $< 10^4$  CFU/mL according to the Food and Drug Administration (FDA) criteria and  $< 10^3$  CFU/mL according to the European Medicines Agency (EMA) criteria on urine culture and negative on repeat blood culture (if positive at baseline).

Microbiologic persistence: the urine culture grows  $\geq 10^4$  CFU/mL for the FDA ( $\geq 10^3$  CFU/mL for the EMA) of any of the baseline pathogen(s) identified at study entry and/or a blood culture demonstrates the same baseline pathogen(s). Patients who are a persistence at EOT will be considered a persistence at TOC.

Microbiologic indeterminate: no follow-up urine culture is available, or the follow-up urine culture cannot be interpreted for any reason, or the follow-up urine culture is considered contaminated. For a baseline blood pathogen, no follow-up blood culture is available.

A per-pathogen microbiological outcome will be determined at the LFU visit. Per-pathogen microbiological outcome categories are sustained eradication, presumed sustained eradication,

continued persistence, recurrence, and indeterminate. A per-pathogen microbiologic outcome of persistence at TOC will be considered a continued persistence at LFU defined as following:

Sustained microbiologic eradication: microbiologic eradication at the TOC Visit and the LFU Visit.

Presumed sustained microbiologic eradication: no urine culture was done at LFU and patient meets clinical criteria for sustained clinical cure.

Microbiologic continued persistence: a per-pathogen microbiologic outcome of persistence at the TOC Visit will be considered a continued persistence.

Microbiologic recurrence: urine culture grows  $\geq 10^4$  CFU/mL for the FDA ( $\geq 10^3$  CFU/mL for the EMA) of any of the baseline pathogen(s) identified at study entry and/or a positive blood culture at any time after documented eradication at the TOC Visit up to and including the LFU Visit.

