Microbiologic indeterminate: no follow-up urine culture is available, or the follow-up urine culture cannot be interpreted for any reason, or the follow-up urine culture is considered contaminated and the patient is not a sustained clinical cure.

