#### **5.1.4.2. Per-Patient Microbiologic Outcome**

An overall per-patient microbiological response at Day 5, EOT, and TOC will be programmatically determined for each patient based on individual outcomes for each baseline pathogen. For a patient to have a microbiological response of eradication, the outcome for each baseline pathogen must be eradicated. If the outcome for any pathogen is persistence, the patient will be considered to have a microbiological response of persistence.

Microbiologic eradication: the outcome of all baseline pathogens must be eradication at the specified visit (Day 5, EOT or TOC).

Microbiologic persistence: the outcome of at least 1 baseline pathogen is persistence.

Microbiologic indeterminate: the outcome of at least 1 baseline pathogen is indeterminate and there is no outcome of persistence for any baseline pathogen.

An overall per-patient microbiological response at LFU will be determined for each patient and will be based on individual outcomes for each baseline pathogen. For a patient to have a microbiological response of sustained eradication, the outcome for each baseline pathogen must be sustained or presumed sustained eradication. If the outcome for any pathogen is recurrence, the patient will be considered to have an unfavorable microbiological response. A per-patient microbiologic outcome of persistence at TOC will be considered a per-patient continued persistence at LFU.

Sustained microbiologic eradication: the outcome of all baseline pathogens must be sustained eradication or presumed sustained eradication.

Microbiologic recurrence: the outcome of at least 1 baseline pathogen is recurrence.

Microbiologic continued persistence: a per-patient microbiologic outcome of persistence at TOC will be considered a per-patient continued persistence.

Microbiologic indeterminate: the outcome of at least 1 baseline pathogen is indeterminate and there is no outcome of recurrence for any baseline pathogen.

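### The late follow-up microbiologic categories leave some patients unclassified and can put others in two categories, so part of the sustained eradication rate is not fixed by the text

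*SAP*

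**What the plan says.** SAP 5.1.4.1 defines five LFU outcomes per baseline pathogen, and the protocol synopsis carries the same definitions.

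- **Sustained eradication:** "microbiologic eradication at the TOC Visit and the LFU Visit".
- **Presumed sustained eradication:** "no urine culture was done at LFU and patient meets clinical criteria for sustained clinical cure". TOC eradication is not stated as a condition.
- **Continued persistence:** "a per-pathogen microbiologic outcome of persistence at the TOC Visit will be considered a continued persistence".
- **Recurrence:** growth of a baseline pathogen at or above threshold, or a positive blood culture, "at any time after documented eradication at the TOC Visit up to and including the LFU Visit".
- **Indeterminate:** the first two limbs are "no follow-up urine culture is available, or the follow-up urine culture cannot be interpreted for any reason". A third limb, for contamination, carries the qualifier at issue: "the follow-up urine culture is considered contaminated and the patient is not a sustained clinical cure".

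SAP 5.1.4.2 builds the patient-level result from these. For sustained eradication, "the outcome of all baseline pathogens must be sustained eradication or presumed sustained eradication". For indeterminate, "the outcome of at least 1 baseline pathogen is indeterminate and there is no outcome of recurrence for any baseline pathogen". There is no residual category.

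Protocol 7.8 says the LFU response is assigned by program. Protocol 6.5 and the notes to SAP Table 1 allow the LFU visit by telephone, in which case no urine is collected. SAP 6.3 lists sustained eradication at LFU, in m-MITT and ME, as an exploratory endpoint.

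**The concern.** A programmed outcome needs rules that give each patient exactly one category. These rules do not, and some of the faults lie on the line between success and non-success. Two patients with the same TOC result and the same clinical course can be treated differently because one telephoned and the other attended and gave a contaminated sample. The first is a presumed eradication; the second has no clear category. Among patients indeterminate at TOC, having no LFU culture can score better than having a clean one.

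At stake is the sustained eradication rate in each arm and the confidence interval for the difference. Someone writing the derivation would have to choose codes that the plan does not supply.

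**Working it through.** The documents give no expected LFU rate and no power calculation, so there is no stated figure to reproduce. The check is of the definitions, followed by the size.

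**Step 1. Classify every combination.** Cross TOC outcome (eradication, persistence, indeterminate) with LFU urine culture (clean, growth of a baseline pathogen, not done, contaminated, otherwise uninterpretable) and sustained clinical cure (yes, no): 3 × 5 × 2 = 30 combinations. Test each against the five categories under three readings of the indeterminate sentence:

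- A: the closing qualifier governs all three culture conditions.
- B: it governs only the contaminated limb.
- C: as B, but a contaminated culture also counts as uninterpretable.

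The problem combinations, leaving TOC persistence aside:

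| TOC | LFU culture | Sustained cure | A | B | C |
|---|---|---|---|---|---|
| Eradication | Contaminated | Yes | none | none | indeterminate |
| Eradication | Otherwise uninterpretable | Yes | none | indeterminate | indeterminate |
| Eradication | Not done | Yes | presumed | presumed and indeterminate | presumed and indeterminate |
| Indeterminate | Clean | Yes or no | none | none | none |
| Indeterminate | Growth | Yes or no | none | none | none |
| Indeterminate | Contaminated | Yes | none | none | indeterminate |
| Indeterminate | Otherwise uninterpretable | Yes | none | indeterminate | indeterminate |
| Indeterminate | Not done | Yes | presumed | presumed and indeterminate | presumed and indeterminate |

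Combinations with no category: 8 under A, 6 under B, 4 under C. TOC persistence always has a category, because it is carried forward as continued persistence.

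Three cases follow.

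- **(a)** TOC eradication, sustained cure, contaminated LFU culture: no category under A or B. Reading C closes it, but the qualifier then does no work.
- **(b)** Sustained cure with no LFU culture: a success and a non-success at once under B and C.
- **(c)** Indeterminate at TOC with a clean LFU culture or with growth: no category under any reading. The same patient with no culture and a sustained cure meets the presumed definition under all three.

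No reading avoids both (a) and (b): A leaves (a) open, C leaves (b) open, and B leaves both.

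**Step 2. Size of case (a).** About 80 patients at 2:1 gives about 53 and 27. Assume 80% reach m-MITT: about 43 and 21, total 64. Assume 3-10% contaminated LFU cultures, and 60-80% of patients both eradicated at TOC and sustained cures. None of these three percentages is in the documents.

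- Low: 64 × 0.03 × 0.60 = 1.2 patients.
- High: 64 × 0.10 × 0.80 = 5.1 patients.

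**Step 3. Effect per patient.** 1/43 = 2.3 points (ETX2514SUL); 1/21 = 4.8 points (placebo).

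**Step 4. Illustration.** Assume 34/43 and 17/21 clear successes, and two further patients in an arm whose code is in doubt.

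| Arm | Coded success | Coded non-success | Dropped |
|---|---|---|---|
| ETX2514SUL | 36/43 = 83.7% | 34/43 = 79.1% | 34/41 = 82.9% |
| Placebo | 19/21 = 90.5% | 17/21 = 81.0% | 17/19 = 89.5% |

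**Step 5. Against the precision.** With 80% success in both arms, the continuity-corrected 95% half-width is 1.96 × √(0.16/43 + 0.16/21) + ½(1/43 + 1/21) = 0.209 + 0.035 = 24.4 points.

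**The case against.** A reader might infer that every unclassified patient can be scored success, non-success or dropped at will, so that the whole rate is arbitrary. The documents do not support that. SAP 5.1.4.2 requires each baseline pathogen to be sustained or presumed eradicated, so a patient in neither category is not a success. The endpoint names m-MITT and ME as its populations, and protocol 9.2.2.3 has the other endpoints analysed like the primary, which keeps indeterminate patients in the denominator. For TOC-indeterminate patients with a clean culture or growth, the literal result is the same as coding them indeterminate, so only a row label changes.

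The support for dropping patients is the general rule in SAP 8.2 that other missing values are not imputed and only observed values are used; the indeterminate-as-failure rule there is stated for the primary outcome. SAP 8.11.4, on exploratory endpoints, is redacted and may settle the denominator. The definitions in 5.1.4 are not redacted.

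A reader might also infer that case (a) is open on any reading. It is not: reading C closes it, and contaminated cultures are plainly indeterminate at TOC. But C makes the qualifier redundant and leaves case (b).

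On size, multiplying 3-10% by all 64 patients gives 1.9 to 6.4, which is only an upper bound, because case (a) also needs TOC eradication and sustained cure.

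Finally, the efficacy analyses are descriptive and the interval is wide. That limits the importance of the fault without removing it.

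**Conclusion.** The point holds as a minor fault in definitions. The five LFU categories are neither exhaustive nor mutually exclusive on any of the three readings. The rate is affected mainly through case (a), case (b) and the no-culture patient in case (c), who scores as a success where a cleanly cultured counterpart does not.

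Case (a) is about 1 to 5 patients across both arms, under the assumptions in step 2. Case (b) cannot be sized: the documents give no rate of telephone visits. Case (c) falls mainly in m-MITT, because ME requires an interpretable TOC urine culture. Each patient recoded moves an arm's rate by about 2 to 5 points, small beside a half-width of about 24 points. Nothing here touches the primary TOC endpoint or the safety objective, and the documents do not support a claim that it does.

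**What to change.** Before unblinding, amend SAP 5.1.4.1 and the matching protocol text:

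- **Presumed sustained eradication:** eradication at TOC, and sustained clinical cure, and an LFU urine culture that was not done, uninterpretable or contaminated.
- **LFU indeterminate:** the same culture conditions without sustained clinical cure, plus every patient indeterminate at TOC whatever the LFU culture shows. These count as non-success and stay in the denominator. Flag those with LFU growth.
- **Existing rules:** keep the carry-forward of TOC persistence and the recurrence definition, and state that both take precedence over the two categories above.
- **Reporting:** show documented and presumed sustained eradication as separate rows.

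The cost is wording and derivation code; no new data, visits or patients are needed. The downside is that counting contaminated cultures as presumed eradication may raise the success rate slightly; the separate rows show by how much. Requiring TOC eradication works the other way, by removing TOC-indeterminate patients with no LFU culture from the successes. Coding contaminated cultures as indeterminate, as at TOC, would also be coherent; what matters is that one rule is fixed in advance.

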#### **5.1.4.2. Per-Patient Microbiologic Outcome**

An overall per-patient microbiological response at Day 5, EOT, and TOC will be programmatically determined for each patient based on individual outcomes for each baseline pathogen. For a patient to have a microbiological response of eradication, the outcome for each baseline pathogen must be eradicated. If the outcome for any pathogen is persistence, the patient will be considered to have a microbiological response of persistence.

Microbiologic eradication: the outcome of all baseline pathogens must be eradication at the specified visit (Day 5, EOT or TOC).

Microbiologic persistence: the outcome of at least 1 baseline pathogen is persistence.

Microbiologic indeterminate: the outcome of at least 1 baseline pathogen is indeterminate and there is no outcome of persistence for any baseline pathogen.

An overall per-patient microbiological response at LFU will be determined for each patient and will be based on individual outcomes for each baseline pathogen. For a patient to have a microbiological response of sustained eradication, the outcome for each baseline pathogen must be sustained or presumed sustained eradication. If the outcome for any pathogen is recurrence, the patient will be considered to have an unfavorable microbiological response. A per-patient microbiologic outcome of persistence at TOC will be considered a per-patient continued persistence at LFU.

Sustained microbiologic eradication: the outcome of all baseline pathogens must be sustained eradication or presumed sustained eradication.

Microbiologic recurrence: the outcome of at least 1 baseline pathogen is recurrence.

Microbiologic continued persistence: a per-patient microbiologic outcome of persistence at TOC will be considered a per-patient continued persistence.

Microbiologic indeterminate: the outcome of at least 1 baseline pathogen is indeterminate and there is no outcome of recurrence for any baseline pathogen.

### **5.1.5. Overall Response**

The primary efficacy outcome is a composite outcome (overall response) and is programmatically determined based on the clinical and microbiologic outcomes based on FDA and EMA criteria as 1 of the following overall responses:

Overall success: a patient who is deemed a clinical cure AND who achieved microbiologic eradication.

Overall failure: a patient who is deemed a clinical failure OR is deemed to have microbiological persistence.

Overall indeterminate: insufficient data are available to determine if the patient is an overall success or failure.

### **5.2. Safety Assessments**

The safety parameters include the incidence, severity, causality, and seriousness of treatment-emergent adverse events (TEAEs) and the evaluation of changes from baseline in safety laboratory test results, ECGs, vital signs, and physical examinations.

#### **5.2.1. Adverse Events**

An adverse event is defined as any untoward medical occurrence in a clinical investigation patient administered a pharmaceutical product, which does not necessarily have a causal relationship with this treatment. An adverse event can therefore be any unfavorable and/or unintended sign (including an abnormal laboratory finding), symptom, or disease temporally associated with the use of an investigational medicinal product, whether or not related to the investigational medicinal product. All adverse events, including observed or volunteered problems, complaints, or symptoms, are to be recorded on the appropriate electronic case report form (eCRF). Adverse events will be monitored and documented from the time of informed consent until study participation is complete. Adverse events will be coded using the Medical Dictionary for Regulatory Activities (MedDRA, Version 20.0).

#### **5.2.2. Clinical Laboratory Evaluations**

Standard clinical laboratory profiles for chemistry will be evaluated at Screening, Day 1, Day 3, Day 5, Day 7, the EOT Visit, the TOC Visit, and the LFU Visit. All Screening laboratories will be performed at the local laboratory and may have been collected as standard of care within 48 hours prior to randomization, with the exception of serum creatinine determination, which must be obtained at the local laboratory within 24 hours of the first dose of study drug. All other samples are to be sent to the central laboratory. The Day 5 safety chemistry panel will be performed at the local laboratory and sent to the central laboratory.

Standard clinical laboratory profiles for hematology will be performed at Screening, Day 1, Day 3, Day 5, Day 7, the EOT Visit, the TOC Visit, and the LFU Visit.

A urinalysis including urine dipstick analysis for leukocytes, nitrites, or a catalase test of the urine specimen, microscopic evaluation, specific gravity, and pH will be performed at Screening, Day 1, Day 3, Day 7, the EOT Visit, the TOC Visit, and the LFU Visit.

A highly sensitive urine or serum pregnancy test will be performed at Screening and at EOT on women of childbearing potential.

Standard of care safety laboratory profiles should also be performed by the local laboratory.

The chemistry, hematology, coagulation and urinalysis parameters assessed in this study include the following:

- Standard safety chemistry panel: alanine aminotransferase (ALT), albumin, alkaline phosphatase (ALP), amylase, aspartate aminotransferase (AST), bicarbonate, blood urea nitrogen, calcium, chloride, creatine kinase, creatinine, estimated glomerular filtration rate, gamma-glutamyl transferase, glucose, inorganic phosphorus, lactate dehydrogenase, lipase, potassium, sodium, total bilirubin, total protein, and uric acid.
- Hematology: hematocrit, hemoglobin, platelets, red blood cell count, white blood cell count and differential, basophils, eosinophils, lymphocytes, mean corpuscular hemoglobin, mean corpuscular hemoglobin concentration, mean corpuscular volume, monocytes, and neutrophils.
- Coagulation: partial thromboplastin time, and prothrombin time.
- Urinalysis: bilirubin, blood, glucose, ketones, leukocyte esterase, microscopy, nitrite, pH, protein, specific gravity and urobilinogen.

Serum (beta human chorionic gonadotropin) or urine pregnancy test will be performed for female patients of childbearing potential only.

All Screening laboratories will be performed at the local laboratory and may have been collected as standard of care within 48 hours prior to randomization, with the exception of serum creatinine determination, which must be obtained at the local laboratory within 24 hours of the first dose of study drug. All other samples are to be sent to the central laboratory. The Day 5 safety chemistry panel will be performed at the local laboratory and sent to the central laboratory.

### **5.2.3. Vital Signs**

Vital signs (including systolic and diastolic blood pressure, heart rate, and respiratory rate) will be taken after at least 5 minutes in a seated position. Vital signs will be recorded at Screening, all days that the patient receives study drug treatment, the EOT Visit, the TOC Visit, and the LFU Visit. Vital signs should be collected at the same time as assessments of signs and symptoms.

### **5.2.4. Electrocardiograms**

Twelve-lead ECGs will be performed at baseline at Screening and repeated as close as possible to the end of the infusion of study drug administration on the day on which the post-dose PK samples are drawn (Day 3, Day 4, or Day 5; day selected at the discretion of the Investigator). All 12-lead ECGs will be performed after the patient has been in a supine position for at least 10 minutes. The value at Screening will be used for assessing the QT interval corrected using Fridericia's formula (QTcF) exclusion criterion. All 12-lead ECGs will be performed and read locally. The following ECG parameters will be recorded:

- Heart rate,
- QRS interval,
- PR interval,

- RR interval,
- QT interval, and
- QTcF interval.

All ECGs will be evaluated for the presence of abnormalities by a qualified local physician. The ECGs will be classified as one of the following:

- Normal,
- Having a not clinically significant abnormality, or
- Having a clinically significant abnormality.

An example of a clinically significant abnormality may be a corrected QTcF >480 msec.

#### **5.2.5. Physical Examinations**

A complete physical examination will be performed at Screening, Day 3, Day 5, Day 7, and the EOT Visit. A limited physical examination will be performed at Day 2, Day 4, Day 6, Day 8 to Day 14 (if EOT has not already occurred), the TOC Visit, and the LFU Visit.

A complete physical examination must include source documentation of skin, head and neck, heart, lung, abdomen, extremities, back/flank/costo-vertebral angle tenderness, and neuromuscular assessments. Weight will be obtained at all complete physical examinations; height will only be collected at Screening. Limited physical examinations are symptom based and do not include weight. When clinically indicated, a prostate exam can be performed, at the discretion of the Investigator.

Physical examinations may be performed at unscheduled time points if deemed necessary by the Investigator.

#### **5.3. Medical History**

Medical/surgical history including urological/renal history inactive conditions diagnosed within the previous 5 years and all active conditions will be collected at screening. Medical/surgical history will be coded using Medical Dictionary for Regulatory Activities (MedDRA, Version 20.0) except for urological/renal history.

#### **5.4. Prior and Concomitant Medications**

All relevant treatments including all antibiotics, prescription and non-prescription medications, herbal medications and vitamin supplements, supportive therapies, and non-pharmacologic treatments received within 14 days before the first dose of study drug and during the study will be collected. The name, route of administration, dose, frequency, indication, and duration of the treatment will be recorded in the eCRF.

Prior and concomitant medication will be coded using the World Health Organization (WHO) Drug Dictionary (March 2017E B2 Version).

Concomitant procedures/non-drug therapies will be coded using MedDRA, Version 20.0.

